6.4. Study Intervention Compliance

All doses of investigational product will be administered by the appropriately designated study staff at the investigator site.

6.5. Concomitant Therapy

Medications/treatments that are taken in the screening period (after informed consent is obtained and before the first dose of study intervention) as well as any medications/treatments taken for the treatment of aplastic anemia at any time prior to the screening visit will be documented as prior medications/treatments. Medications/treatments taken after the first dose of study intervention has been administered will be documented as concomitant medications/treatments. Any medication or vaccine (including over-the-counter or prescription medicines, vitamins, and/or herbal supplements) that the participant is receiving at the time of enrollment or receives during the study must be recorded along with:

- Reason for use
- Dates of administration including start and end dates
- Dosage information including dose and frequency

The Pfizer Medical Monitor or designee should be contacted if there are any questions regarding concomitant or prior therapy.

6.5.1. Permitted Concomitant Medications

For the purposes of this protocol, dietary supplements are defined as vitamins, minerals, and purified food substances with pharmaceutical properties. Vitamins, minerals and purified food substances are allowed in amounts not known to be associated with adverse effects (such as hypervitaminosis).

A participant who is receiving a permitted concomitant medication for any reason must be on a locally-approved medication and dose for the treated indication, and this must be documented on the case report form (CRF).

Participants should report any changes to permitted medications during the study to the investigator as soon as they occur. Medication changes must be documented in the participant's record and CRF.

Unless a prohibited medication or treatment, participants may be administered any other medications necessary for the treatment of concomitant medical disorders as deemed necessary by the treating physician. Following Day 1, addition of concomitant medications or any change in the dosage should be limited to those considered medically essential.

Premedication is recommended for all participants, consistent with institutional guidelines, and may include an antihistamine, anti-inflammatory agent, or pain reliever.

It is available to administer the following drugs according to the patient's condition with reference [Reference Guide for Management of Aplastic Anemia, Revised in 2018] or institutional guidelines:

- Cyclosporine
- Corticosteroid (e.g. prednisolone)
- Diphenhydramine and acetaminophen
- Iron chelation therapy
- Antibacterial, antifungal and antiviral drugs
- Blood transfusion (erythrocyte, platelet transfusion)

6.5.2. Permitted Concomitant Medications only when necessary

The following medications are permitted to use only when necessary.

- G-CSF
- Eltrombopag, Lomiprost
- Anabolic steroids

6.5.3. Prohibited Concomitant Medications

Participants will abstain from all prohibited medications as described below in this section. Medically necessary medications should not be discontinued without prior evaluation of acceptable alternatives, including consultation with prescribing health professional.

Participants should be instructed at each visit to contact the study site investigator promptly if there are any intended changes or additions to concomitant medications.

Prohibited Concomitant Medications/Treatments:

The following medications and treatments are prohibited for use during the study.

Participants who are treated with any prohibited medication or treatment during the course of the study may be discontinued after discussion with the sponsor. NOTE: Examples provided do not represent an all-inclusive list of medications and treatments. If there is a question about whether a particular medication is prohibited, the medication should be discussed with the sponsor.

- Medications and treatments that could affect aplastic anemia:
 - ATG (horse or rabbit)

- Lymphocyte-depleting agents/therapies, including both non-B-cell selective and B-cell-depleting agents (e.g., alefacept, alemtuzumab, rituximab)
- Immunosuppressants except for cyclosporine A, corticosteroids (e.g., azathioprine, methotrexate, sulfasalazine, mycophenolate mofetil).
- Medications with potential safety concerns:
 - Investigational drugs
 - Live (attenuated) vaccines: prohibited within the 6 weeks prior to the first dose of study intervention, during the study, and for 6 months after the last dose of study intervention.

6.6. Dose Modification

Dose modification of the study intervention is not permitted in this study.

6.7. Intervention After the End of the Study

No intervention will be provided to study participants at the end of the study.

7. DISCONTINUATION OF STUDY INTERVENTION AND PARTICIPANT DISCONTINUATION/WITHDRAWAL

7.1. Discontinuation of Study Intervention

In rare instances, it may be necessary for a participant to permanently discontinue investigational product. If investigational product is permanently discontinued, the participant will remain in the study to be evaluated for the assessments at the Early Termination (ET) and Follow-up visits (per [Schedule of Activities \(SoA\)](#)).

Note that discontinuation of investigational product does not represent withdrawal from the study.

See the [Schedule of Activities \(SoA\)](#) for data to be collected at the time of intervention discontinuation and follow-up and for any further evaluations that need to be completed.

7.2. Participant Discontinuation/Withdrawal From the Study

A participant may withdraw from the study at any time at his/her own request, or may be withdrawn at any time at the discretion of the investigator for safety, behavioral, compliance, or administrative reasons.

At the time of discontinuing from the study, if possible, an early discontinuation visit should be conducted. See the [Schedule of Activities \(SoA\)](#) for assessments to be collected at the time of study discontinuation and follow-up and for any further evaluations that need to be completed.

The early discontinuation visit applies only to participants who are assigned to the investigational product and then are prematurely withdrawn from the study. Participants should be questioned regarding their reason for withdrawal. The participant will be permanently discontinued both from the study intervention and from the study at that time.

If a participant withdraws from the study, he/she may request destruction of any remaining samples, but data already generated from the samples will continue to be available, and may be used to protect the integrity of existing analyses. The investigator must document any such requests in the site study records.

If the participant withdraws from the study and also withdraws consent (see below) for disclosure of future information, no further evaluations should be performed and no additional data should be collected. The sponsor may retain and continue to use any data collected before such withdrawal of consent.

When a participant withdraws from the study because of an SAE, the SAE must be recorded on the CRF and reported on the Clinical Trial (CT) SAE Report.

Lack of completion of all or any of the withdrawal/early termination procedures will not be viewed as protocol deviations so long as the participant's safety was preserved.

Withdrawal of Consent:

Participants who request to discontinue receipt of study treatment will remain in the study and must continue to be followed for protocol-specified follow-up procedures. The only exception to this is when a participant specifically withdraws consent for any further contact with him or her or persons previously authorized by the participant to provide this information. Participants should notify the investigator in writing of the decision to withdraw consent from future follow-up, whenever possible. The withdrawal of consent should be explained in detail in the medical records by the investigator, as to whether the withdrawal is only from further receipt of investigational product or also from study procedures and/or posttreatment study follow-up, and entered on the appropriate CRF page. In the event that vital status (whether the participant is alive or dead) is being measured, publicly available information should be used to determine vital status only as appropriately directed in accordance with local law.

7.3. Lost to Follow-up

A participant will be considered lost to follow-up if he or she repeatedly fails to return for scheduled visits and is unable to be contacted by the study site.

The following actions must be taken if a participant fails to return to the clinic for a required study visit:

- The site must attempt to contact the participant and reschedule the missed visit as soon as possible and counsel the participant on the importance of maintaining the

assigned visit schedule and ascertain whether or not the participant wishes to and/or should continue in the study;

- Before a participant is deemed lost to follow-up, the investigator or designee must make every effort to regain contact with the participant (where possible, 3 telephone calls and, if necessary, a certified letter to the participant's last known mailing address or local equivalent methods). These contact attempts should be documented in the participant's medical record;
- Should the participant continue to be unreachable, he/she will be considered to have withdrawn from the study.

Discontinuation of specific sites or of the study as a whole is handled as part of [Appendix 1: Regulatory, Ethical, and Study Oversight Considerations](#).

8. STUDY ASSESSMENTS AND PROCEDURES

The investigator (or an appropriate delegate at the investigator site) must obtain a signed and dated ICD before performing any study-specific procedures.

Study procedures and their timing are summarized in the [Schedule of Activities \(SoA\)](#). Protocol waivers or exemptions are not allowed.

Immediate safety concerns should be discussed with the sponsor immediately upon occurrence or awareness to determine if the participant should continue or discontinue study intervention.

Adherence to the study design requirements, including those specified in the SoA, is essential and required for study conduct.

All screening evaluations must be completed and reviewed to confirm that potential participants meet all eligibility criteria. The investigator will maintain a screening log to record details of all participants screened and to confirm eligibility or record reasons for screening failure, as applicable.

Procedures conducted as part of the participant's routine clinical management (e.g., blood count) and obtained before signing of the ICD may be utilized for screening or baseline purposes provided the procedures met the protocol-specified criteria and were performed within the time frame defined in the SoA.

Every effort should be made to ensure that protocol-required tests and procedures are completed as described. However, it is anticipated that from time to time there may be circumstances outside the control of the investigator that may make it unfeasible to perform the test. In these cases, the investigator must take all steps necessary to ensure the safety and well-being of the participant. When a protocol-required test cannot be performed, the investigator will document the reason for the missed test and any corrective and preventive

actions that he or she has taken to ensure that required processes are adhered to as soon as possible. The study team must be informed of these incidents in a timely manner.

The total blood sampling volume for individual participants in this study is approximately 60 mL. The actual collection times of blood sampling may change. Additional blood samples may be taken for safety assessments at times specified by Pfizer, provided the total volume taken during the study does not exceed 550 mL during any period of 60 consecutive days.

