5.1. Inclusion Criteria

Participants are eligible to be included in the study only if all of the following criteria apply:

Age and Sex:

1. Male or female participants between the ages of 2 years and more, inclusive, at Visit 1 (Screening).
 - Refer to Appendix 4 for reproductive criteria for male (Section 10.4.1) and female (Section 10.4.2) participants.

Type of Participant and Disease Characteristics:

2. Participants who are willing and able to comply with all scheduled visits, treatment plan, laboratory tests, lifestyle considerations, and other study procedures.
3. Have a clinical diagnosis of aplastic anemia by bone marrow aspiration/biopsy findings and/or magnetic resonance imaging (MRI) etc.
4. Must meet the following criteria of moderate and above aplastic anemia (Stage 2b and above, see [Table 2](#)):

Informed Consent:

5. Capable of giving signed informed consent/assent as described in Appendix 1, which includes compliance with the requirements and restrictions listed in the informed consent document (ICD)/assent document and in this protocol.

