6.1.1. Administration

Participants will undergo PF-06462700 skin test. Those with a positive skin test will not be administered PF-06462700.

PF-06462700 will be administered at a dose of 40 mg/kg/day for 4 days. PF-06462700 will be infused intravenously over no less than 4 hours. Infusion times may be extended up to 24 hours (including dilution/preparation time) to improve tolerance if necessary.

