8.2. Safety Assessments

Planned time points for all safety assessments are provided in the [Schedule of Activities \(SoA\)](#). Unscheduled clinical laboratory measurements may be obtained at any time during the study to assess any perceived safety concerns.

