8.2.1. Physical Examinations

Investigators should pay special attention to clinical signs related to previous serious illnesses.

Weight (kgs) will be measured and recorded in the source document at various time points according to [Schedule of Activities \(SoA\)](#).

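### The 550 mL per 60 days blood-draw ceiling is not scaled to weight, so it gives small children, who are eligible from age 2, no practical protection

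*Protocol*

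**What the plan says.** Protocol Section 8 gives the planned volume: "The total blood sampling volume for individual participants in this study is approximately 60 mL". It then opens the door to more, at the sponsor's choice of timing, and attaches one condition: "provided the total volume taken during the study does not exceed 550 mL during any period of 60 consecutive days". The ceiling applies to the total drawn. It has no per-kilogram term and no separate figure for children.

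Children are clearly in scope. Section 5.1, criterion 1, sets the minimum age at 2 years, with no minimum weight, and criterion 5 refers to the "requirements and restrictions listed in the informed consent document (ICD)/assent document and in this protocol". The estimand population in Section 9.1.1 has the same age floor, and Section 10.1.3 provides for consent by a parent or guardian.

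Sampling beyond the schedule is foreseen elsewhere too. Section 8.2 states: "Unscheduled clinical laboratory measurements may be obtained at any time during the study to assess any perceived safety concerns". Section 8.2.4 calls for clinically significant abnormal tests to be repeated, and Appendix 5 describes further blood tests for a suspected liver injury. The SAP carries over the unscheduled-testing provision (Section 3.5.2) and adds no volume limit.

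**The concern.** The Section 8 sentence is the only numeric limit on blood volume in either document. A fixed volume that is moderate for an adult is a much larger share of a small child's blood. The protocol already scales the drug to body size ("PF-06462700 will be administered at a dose of 40 mg/kg/day for 4 days"), but the sampling limit does not follow.

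The population makes this worth correcting. Entry requires Stage 2b disease or above, and Stages 2b and 3 are defined by a need for red cell transfusion (Table 2). Participants with marrow failure are poorly placed to replace blood that is drawn. What is at stake is participant safety only.

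**Working it through.** **Inputs from the documents**
- Ceiling: 550 mL in any 60 consecutive days (Protocol Section 8).
- Planned total: about 60 mL over the study (Protocol Section 8).
- Minimum age: 2 years, no weight floor (Protocol Section 5.1).

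The documents give no derivation for the 550 mL or the 60 mL, so there is no stated calculation to reproduce.

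**Assumptions not in the documents**
- Body weights of 10 to 20 kg for young children and 50 to 70 kg for adults.
- Circulating blood volume of 70 to 80 mL/kg.

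**Step 1: the ceiling and the plan per kilogram.** Ceiling per kg = 550 / weight. Planned volume per kg = 60 / weight. Share of blood volume = 550 / (weight × 80) to 550 / (weight × 70).

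| Assumed weight | Ceiling, mL/kg | Ceiling as share of blood volume | Planned 60 mL, mL/kg |
|---|---|---|---|
| 10 kg | 55.0 | 69%–79% | 6.0 |
| 15 kg | 36.7 | 46%–52% | 4.0 |
| 20 kg | 27.5 | 34%–39% | 3.0 |
| 60 kg | 9.2 | 11%–13% | 1.0 |

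Relative to 60 kg, the ceiling per kg is 55.0 / 9.17 = 6.0 times as high at 10 kg and 36.7 / 9.17 = 4.0 times as high at 15 kg. Even at 20 kg it is 27.5 / 9.17 = 3.0 times as high, so the conclusion does not hang on the 10 kg figure.

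**Step 2: a limit on the protocol's own scale.** 550 / 60 = 9.17, rounded down to 9 mL/kg. With an adult of 70 kg or 50 kg as reference, 550 / 70 = 7.9 and 550 / 50 = 11.0, so the range is about 8 to 11 mL/kg. At 9 mL/kg the allowance is 90 mL at 10 kg (80 to 110 mL over the range), 135 mL at 15 kg and 180 mL at 20 kg. The two limits meet at 550 / 9 = 61.1 kg.

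**Step 3: does scheduled sampling fit?** If all 60 mL fell in one 60-day window, it would still be under 90 mL at 10 kg. It would fit down to 60 / 9 = 6.7 kg. This bound needs no assumption about the volume of each draw.

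For a closer picture, the Schedule of Activities has 11 hematology draws: screening and Days 1, 4, 8, 15, 29, 43, 57, 71, 85 and 169. At nominal days, at most 7 fall in one 60-day window, or 8 if screening is on Day −3 or later and the Day 1 draw is not omitted. With equal volumes (60 / 11 = 5.45 mL each) that is 38 to 44 mL. Equal volumes are only a rough assumption, because the screening draw also carries the viral serology.

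**The case against.** The strongest reply is that the ceiling will almost never be approached. At about 5.45 mL per draw, 550 mL would take 550 / 5.45, or about 100 draws in 60 days, against 7 or 8 scheduled. The target is 3 participants, although more may be assigned (Section 9.2). Incidence peaks in the 10s to 20s and the 70s to 80s (Section 2.2.2.3), and nothing shows that a 10 to 15 kg child is expected. All of this stands, and it is why the point is minor. It does not rescue the ceiling, which exists for the case where the plan is exceeded.

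A second reply is that the unscheduled tests, repeats and liver work-up are mostly clinically indicated and led by the investigator, whereas the clause at issue concerns samples at times the sponsor specifies. That is fair, and it shapes the remedy. A tighter limit should bear on scheduled and sponsor-specified sampling. It should not hold back tests a sick child needs, nor lift the 550 mL ceiling that now covers them.

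A third reply is that a pediatric limit may sit elsewhere. The laboratory manual (Section 8.2.4) and the consent and assent documents are not available here, and Section 10.1.1 requires ethics committee approval. A reader might infer that the trial has no pediatric limit at all. The documents do not support that: they show only that the protocol and SAP state none.

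**Conclusion.** The point holds as a minor participant-safety gap in Protocol Section 8. The stated ceiling allows 55 mL/kg at 10 kg and 37 mL/kg at 15 kg, against 9.2 mL/kg at 60 kg, and so does not act as a limit for the smallest eligible participants. The per-kilogram figures rest on assumed weights. The blood-volume shares rest also on an assumed 70 to 80 mL/kg.

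Two stronger readings should be resisted. One is that children will have dangerous volumes drawn: the plan is about 60 mL in total, or 6 mL/kg at an assumed 10 kg over the whole study. The other is that sampling would distort the hematologic response or transfusion endpoints: nothing in the documents supports that.

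**What to change.** In Protocol Section 8, keep the 550 mL ceiling on total volume for everyone, with no exemption, and add one sentence:

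> *For pediatric participants, scheduled study samples plus additional samples specified by the sponsor must also not exceed 9 mL/kg in any period of 60 consecutive days, or the applicable IRB/EC or institutional pediatric limit if stricter, based on the most recent weight (a weight from the medical record or measured at screening if no study weight is yet available).*

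Clinically indicated tests, such as the Appendix 5 liver work-up, stay under the 550 mL ceiling only. They are neither newly restricted nor newly uncapped. The weight fallback is needed because the Schedule of Activities has no screening weight: weight is first scheduled at Day 1, where a value from the preceding 3 days may be used.

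The 9 mL/kg is the existing ceiling rescaled from an assumed 60 kg adult (8 to 11 mL/kg for 70 to 50 kg). It is not a validated pediatric threshold, so a sponsor with an established pediatric limit should use that figure instead. If the limit adopted is below 6 mL/kg, scheduled sampling at 10 kg must be checked against it.

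The cost is one added sentence, with ethics committee approval of the amendment, a matching check of the laboratory manual, and a weight on file before the screening draw in children. The downside is fewer optional extra samples in small children. Adults are unaffected.

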8.1. Efficacy Assessments

8.1.1. Hematologic response

Hematologic response at Weeks 12 and 24

“Effective” when 2 or more of the following criteria:

- Absolute neutrophil count $\geq 500/\mu\text{L}$
- Platelet count $\geq 20,000/\mu\text{L}$
- Reticulocyte count $\geq 60,000/\mu\text{L}$

Improvement in counts that are dependent upon exogenously administered growth factors or transfusion will not be considered as fulfilling response criteria.

For subjects of Stage 2b or 3 (see [Table 2](#)) at the baseline*, hematological response will be “effective” when the above-mentioned criteria are met, and Stage is improved at the same time. (*If the baseline assessment is omitted [[Section 1.3](#)], severity at the screening will be referred.)

8.1.2. Hematological test values

Hematological test values (absolute neutrophil count, platelet count and reticulocyte count) will be evaluated at Weeks 12 and 24. These values will also be evaluated at Day 4 and at Weeks 1, 2, 4, 6, 8 and 10. In case of early termination (ET), these values will be evaluated at ET and follow-up for ET.

8.1.3. Transfusion independence

Transfusion independence will be evaluated at Weeks 12 and 24.

8.1.4. Survival status

During the study period, the survival status of each participant will be recorded.

8.2. Safety Assessments

Planned time points for all safety assessments are provided in the [Schedule of Activities \(SoA\)](#). Unscheduled clinical laboratory measurements may be obtained at any time during the study to assess any perceived safety concerns.

8.2.1. Physical Examinations

Investigators should pay special attention to clinical signs related to previous serious illnesses.

Weight (kgs) will be measured and recorded in the source document at various time points according to [Schedule of Activities \(SoA\)](#).

